Fibrinogen Pre transfusion	Fibrinogen (number)		
Fibrinogen Post transfusion	Fibrinogen (number)		
International Normalized Ratio (INR) Pre transfusion	International Normalized Ratio (INR) (number)		
International Normalized Ratio (INR) Post transfusion	International Normalized Ratio (INR) (number)		
Procedure performed	esophagogastroduodenoscopy = 1, colonoscopy = 2, neurosurgical procedures = 3, other endoscopy procedures = please type out procedure (e.g. endoscopic ultrasound)		
Blood product use prior to procedure	Number of Units		
Type of blood product given prior to procedure	Fresh Frozen Plasma (FFP) = 1, platelets = 2, cryoprecipitate = 3		
Packed Red Blood Cells (pRBC) use post-procedure	Number of units		
Total blood product use post-procedure	Number of units		
Significant blood loss peri-procedure	No = 0, Yes = 1		
Bleeding event 24 hours post-procedure	No = 0, Yes = 1		
Hospital Length of Stay	Number of Days		
Cost	Total cost of ROTEM reagents and supplies used and		
	lab tests (number)		

Division of Gastroenterolgoy, Hepatology & Nutrition Confidential

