Several studies utilizing ROTEM have shown that maximum clot firmness and fibrinogen levels are reliable predictors of perioperative bleeding complications and need for massive transfusions of blood products [3]. In patients undergoing liver transplantation, use of ROTEM guided hemostatic therapy correctly predicted hypofibrinogenemia, thrombocytopenia, and decreased clot firmness [4]. Furthermore, researchers suggest that while PT and INR are used as a prognostic indicator and to guide blood product management, that these tests are poor predictors of bleeding risk in liver disease [5]. This is an important realization, which challenges the current practice of correcting an abnormal INR with fresh frozen plasma prior to invasive procedures, even though INR cannot accurately predict bleeding risk, as it measures only one of the many components of coagulation and clot stability. Used in other scenarios where coagulopathy is encountered, studies have revealed the utility of ROTEM use in liver transplantation, significant hemorrhage, cardiac surgery, and detecting coagulation disorders in trauma [6].

WEXNER MEDICAL CENTER

Application of ROTEM hemostatic therapy and algorithm-guided blood products resuscitation before and during endoscopies may lead to more judicious use of blood products for cirrhotic patients with coagulopathy, as point of care testing will reveal information on the coagulation status of the patient to guide transfusions. In cardiac surgery patients who also had coagulopathy, point of care ROTEM testing resulted in lower cumulative blood product usage (including packed red blood cells, pooled platelets, and fresh frozen plasma), as well as lower post-operative mechanical ventilation time, length of intensive care unit stay, and six month mortality [7]. Cirrhosis-related coagulopathies represent an even more significant derangement in natural clotting and anticoagulation factors, and ROTEM may provide a more holistic approach to understanding where a particular patient lies on the spectrum from a high bleeding risk to a high clotting risk.

III. Procedures

A. Research Design

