The objective of this study is to investigate blood product use, bleeding events, hospital length of stay, and health care costs in hospitalized patients with cirrhosis and coagulopathy undergoing endoscopy or neurosurgical procedures utilizing ROTEM compared to conventional therapy. Data will be extracted from charts in the electronic medical record (IHIS). Data from charts will be used to construct a secure database of information on risk factors and pre-procedure testing (see Appendix 1). This database will allow analysis of clinical outcomes in patients with cirrhosis undergoing an endoscopic or surgical procedure.

In this prospective study, patients will be randomized into one of two groups:

-Study Group: those who receive blood product transfusions based on ROTEM-guided protocol (Appendix 2). -Control Group: those who receive blood product transfusions based on conventional, laboratory-guided parameters (Appendix 3).

The randomization list will be computer-generated using a balanced allocation ratio of 1:1. The endoscopist or surgeon performing the procedure will be blinded to the patient's group.

B. Hypothesis

The ROTEM- guided transfusion protocol will significantly decrease blood product usage without any increase in procedural bleeding complications versus the conventional, laboratory-based transfusion protocol in patients with cirrhosis undergoing endoscopy and neurosurgical procedures.

C. Objectives

Primary Objective

To compare the total amount of pre-procedure blood products transfused between the ROTEM-guided transfusion protocol and conventional, laboratory-based transfusion protocol in patients undergoing endoscopy and neurosurgical procedures. Endoscopy procedures include esophagogastroduodenoscopy, colonoscopy, flexible sigmoidoscopy, endoscopic retrograde cholangiopancreatography, and endoscopic ultrasound. Neurosurgical procedures may include bedside procedures (e.g. placement of an external ventricular drain or placement of an intracranial pressure monitor), or any neurosurgical cranial or spinal procedure that occurs in the operating room

WEXNER MEDICAL CENTER

during the patient's admission (e.g. craniotomy for evacuation of hematoma or a spinal fusion procedure to address spinal instability).

Secondary Objectives

- 1. Compare the rate of bleeding events between ROTEM vs. conventional therapy:

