 - Clinically significant peri-procedure blood loss as documented by the endoscopist or surgeon performing the procedure
 - Major bleeding during the 24 hours post-procedure, defined as a decrease in hemoglobin of ≥ 2 g/dL or requiring a transfusion of ≥ 2 units of packed red blood cells.
- 2. Compare length of stay between ROTEM vs. conventional therapy
- 3. Compare hospitalization costs between ROTEM vs. conventional therapy

D. Sample

202 patients with cirrhosis and coagulopathy who are undergoing an endoscopic or neurosurgical procedure, at The Ohio State University Wexner Medical Center will be enrolled into the study using the inclusion/exclusion criteria below. Coagulopathy will be corrected by ROTEM-guided transfusion protocol (Appendix 2) or conventional, laboratory-based transfusion protocol (Appendix 3) prior to procedure using a 1:1 randomization.

For the primary aim, a total sample size of 202 patients (101 patients in both the non-ROTEM and ROTEM groups) is required to achieve 80% power for a two-sample t-test to detect a 100% increase in the geometric mean of the non-ROTEM group over the ROTEM group. Significance is defined as a two-sided p-value of less than 0.05. This calculation was based off of pilot data which contained 8 ROTEM and 8 non-ROTEM patients. The secondary aim, demonstrating that the proportion of bleeding events in ROTEM patients is equivalent to or less than the proportion in non-ROTEM patients requires a sample size of 446 patients per group. This calculation assumed that both ROTEM and non-ROTEM patients experience a bleeding event 10% of the time. It was further assumed that the proportion of bleeding events in the ROTEM group will be considered to be equivalent to that of the non-ROTEM group if the proportion is no more than 5% larger. The secondary aim is exploratory in nature for the purposes of this protocol as the sample size for the current study is only 202 patients.

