The requested data fields include demographic data, clinicopathologic data, and procedure/operative reports. Please see Appendix 1 for all variables that will be extracted from charts. Any PHI that is collected as part of this prospective study will be maintained in the secure database.

Standard coagulation tests

Conventional coagulation tests (hemoglobin, platelet count, fibrinogen concentration, INR, aPTT, and PT) will be performed in both groups (ROTEM vs. conventional therapy) at two fixed time points (enrollment and within 3 hours after transfusion [which is also within 12 hours of procedure]) in order to compare both groups reliably. Transfusion of blood products (if indicated per the transfusion protocols) will occur within 24 hours of enrollment in both groups. In the post-procedure setting, tests will be performed if any bleeding occurs per the treating physician's discretion.

ROTEM

ROTEM will be performed according to the manufacturer's instruction, using equipment provided by Tem International GmbH. All tests will be performed at the bedside by a clinical perfusionist or study staff member trained to perform ROTEM. The point of care treatment will be guided with the Spine Surgery Algorithm based on the EXTEM, INTEM, FIBTEM and HEPTEM assays. ROTEM will be performed in both groups (ROTEM vs. conventional therapy) at two fixed time points (enrollment and within 3 hours after transfusion [which is also within 12 hours of procedure]) in order to compare both groups reliably.

The Ohio State University

WEXNER MEDICAL CENTER

F. Data Analysis

We will analyze blood product usage, peri- and post-procedure bleeding events, and hospital length of stay comparing ROTEM-guided transfusion protocol versus conventional, laboratory-based transfusion protocol. We will calculate any significant differences between these two cohorts using standard T-Test and multivariate analysis (ANOVA) with support from our Internal Medicine biostatistician.

All study patients will be continuously monitored by the study PI and sub-I's on the inpatient hepatology services. Safety monitoring will be performed on an ongoing basis throughout the entirety of the study. Based on our retrospective study using ROTEM in liver transplantation, we expect FFP transfusion rate to decrease by 50% and cryoprecipitate transfusion rate to increase in the ROTEM group with an overall decrease in blood product use. We expect bleeding rates to be similar in both groups.

IV. References

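### Secondary objective 3 compares hospitalization costs, but the only cost variable defined is testing cost, which the schedule makes equal in both arms

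*Protocol*

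**What the plan says.** Section III.C, secondary objective 3: "Compare hospitalization costs between ROTEM vs. conventional therapy". Section III.A sets the wider aim as "blood product use, bleeding events, hospital length of stay, and health care costs in hospitalized patients" with cirrhosis and coagulopathy.

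The Cost row of Appendix 1 reads "Total cost of ROTEM reagents and supplies used and" and continues on the next line with lab tests, recorded as a number. It is the only cost row.

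On data sources, section III.A says "Data will be extracted from charts in the electronic medical record (IHIS"), and section III.E says "Please see Appendix 1 for all variables that will be extracted from charts".

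Section III.E schedules ROTEM and the conventional coagulation tests for both groups at enrollment and again after transfusion, before the procedure. Appendix 4 shows one schedule with no split by arm.

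Section III.F lists blood product use, bleeding events and length of stay for analysis, but not cost. The SAP names no cost analysis.

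**The concern.** The objective and the variable describe different quantities. Hospitalization cost includes the stay, the products, the procedure and the treatment of complications. The Cost row holds only tests.

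The gap matters because the savings the protocol anticipates lie outside that row. Section III.F says "we expect FFP transfusion rate to decrease by 50" percent, with cryoprecipitate rising and total product use falling. The Background cites a cardiac-surgery trial in which "point of care ROTEM testing resulted in lower cumulative blood product usage", "as well as lower post-operative mechanical ventilation time, length of intensive care unit stay, and six month mortality". Product and stay costs are where an economic effect would be expected, and neither enters the field.

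If the Cost field is used for objective 3, a testing-cost difference near zero could be presented as evidence that hospitalization costs are similar, while product and bed-day costs differ.

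**Working it through.** The documents give no cost figure, unit price or cost-based sample size, so there is no stated result to reproduce. The check compares objective, field and schedule, with simple accounting.

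**1. What the field covers.** Appendix 1 has 23 rows, counting the split Race line once; 1 is a cost row. Set against the components of a hospitalization cost:

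| Component | In the Cost field? | Quantity elsewhere in Appendix 1 | Unit cost given? |
|---|---|---|---|
| Testing | Yes | – | No |
| Blood products | No | Pre-procedure units and a type code; post-procedure pRBC units and total units | No |
| Bed days | No | Length of stay in days | No |
| Procedure | No | Procedure code | No |
| Bleeding treatment | No | Two yes/no bleeding items; post-procedure pRBC units | No |

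The field covers 0 of the 4 non-testing components. Quantities exist for 3 of the 4 and partly for the fourth. Unit costs exist for none.

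**2. Scheduled difference between arms.** Let R be the cost of one ROTEM panel and L the cost of one conventional lab panel.

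- ROTEM assays per patient: 4 assays × 2 time points = 8 in each arm.
- Lab tests per patient: 6 named in III.E × 2 = 12 in each arm (5 named in the Appendix 4 footnote × 2 = 10).
- Scheduled cost: 2(R + L) in the ROTEM arm and 2(R + L) in the control arm.
- Difference: 2(R + L) − 2(R + L) = 0, whatever R and L are.

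**3. Where a realized difference could come from.** Tests after bleeding are at the treating physician's discretion, though III.F expects similar bleeding rates. The second test set is timed from transfusion, and transfusion is given only when the arm's protocol calls for it. The documents do not say whether untransfused patients have that set. Assume they do not, and let q be the share transfused in an arm:

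- Mean scheduled cost in an arm: (1 + q)(R + L).
- Difference, ROTEM minus control: (q_ROTEM − q_control)(R + L).
- Range: from −(R + L) to +(R + L), that is, at most one test set per patient in either direction.

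Repeat testing within the Appendix 2 or 3 algorithms cannot be checked, because their content is not visible in the text available. Any difference from these three sources is still testing cost.

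**4. Can cost be rebuilt from the other rows?** Only in part. Pre-procedure use is a single unit count beside a type code. If a patient receives more than one product, the units cannot be split by type as the row is written. Post-procedure, only pRBC is separated from the total. Since III.F expects FFP to fall and cryoprecipitate to rise, a cost built from these rows depends on the split that they do not clearly record.

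**The case against.** The strongest reply is that the Cost row is not the whole dataset. Product units, procedure and length of stay are collected, and hospitalization cost could be built from them with unit costs, the Cost row supplying the testing part. The statement about Appendix 1 also covers only variables taken from charts, so a billing source is not ruled out. Both points stand as possibilities. Neither is stated as the plan: no unit costs, costing method or billing source is named, and the product rows do not clearly support costing by type.

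Two stronger readings are tempting, and the documents do not support them.

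- A reader might infer that the Cost field must come out equal in the two arms, so that the expected fall in FFP use would leave it unchanged. Only the schedule is equal. If fewer patients were transfused, fewer might have the second test set, and the field could move.
- A reader might infer that the trial will report testing cost as hospitalization cost. Neither section III.F nor the SAP specifies any cost analysis, so this is a risk if the field is used for objective 3, not a planned result.

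**Conclusion.** The mismatch holds. Objective 3 names hospitalization costs, and the one variable defined for cost measures testing, with a scheduled between-arm difference of 0. This is more than missing detail, because the variable that is specified measures a different quantity.

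The size in money is unknown, since no unit costs are given. The zero applies to the schedule as printed for all patients. Under the assumption that untransfused patients skip the second set, the mean difference could reach one test set per patient in either direction, and it would remain a testing cost. Because control patients also receive ROTEM by protocol, the field would not show the added testing cost of a ROTEM strategy over usual care either.

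Severity is minor. One secondary objective is affected; the primary, bleeding and length-of-stay results, the sample size and the significance level are not.

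**What to change.** 1. Redefine the Appendix 1 Cost field as total index-hospitalization cost. Take it from hospital billing, including blood products, or compute it as collected quantities (product units by type, bed days, procedure) times unit costs fixed in advance. The second route requires recording pre- and post-procedure units separately for each product.
2. Hold the cost of protocol-driven study tests in a separate field, with one pre-specified rule for how it counts in each arm. Several costing conventions would serve; what matters is that one is fixed in advance.
3. Add to section III.F the between-arm difference in mean cost with a 95% confidence interval.

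If this cannot be done, rename objective 3 as a comparison of testing costs, align the aim in section III.A, and make no claim about hospitalization cost.

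The cost is one billing extract or one unit-cost list, plus edits to Appendix 1 and III.F. If billing is used, it must be shown to be accessible, which the documents do not establish. No added patient contact is needed. The fallback is a text edit only.

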Appendix 2: ROTEM Transfusion Protocol

[figure not shown]

Page 9 of 9

Division of Gastroenterolgoy, Hepatology & Nutrition Confidential

Appendix 3: Conventional, Laboratory-Based Transfusion Protocol

THE OHIO STATE UNIVERSITY WEXNER MEDICAL CENTER

Appendix 4: Schedule of Events

	Enrollment	< 3 hours after transfusion and < 12 hours of procedure	Peri-procedure	24 hours post- procedure
Consent	\checkmark			
Randomization	\checkmark			
ROTEM ¹	✓	✓		
Blood Collection ²	✓	✓		
Assess for Bleeding			\checkmark	✓
¹ Includes INTEM, EXTEM, HEPTEM, FIBTEM; ² Includes fibrinogen, PT/INR/aPTT, Hemoglobin;

COVER LETTER

Document date: 3/10/2020

Comparison of Blood Product Use and Bleeding Events During and After Endoscopic or Neurosurgical Procedures in Patients with Cirrhosis and Coagulopathy: Rotational Thromboelastometry Versus Conventional Therapy

NCT02457403

Statistical Analysis

Our sample size of thirty-four patients per group was based on a pilot project at OSUWMC that evaluated a total of sixteen patients. The same variables were studied in the pilot project, but no statistically significant results were found. We powered our study for the primary outcome of intra-operative blood loss based on the results of the pilot data.

Patient characteristics and laboratory values were compared between the two groups. Fisher exact tests were used to test for significant differences between the ROTEM and conventional coagulation groups with discrete variables such as race and gender. With continuous variables that were approximately normally distributed (BMI, MELD, and age), two-sample t-tests were used to test for significant differences between groups. Due to the non-normality of all laboratory values and ICU length of stay, nonparametric Wilcoxon rank-sum tests were used to test for significance.

Blood product usage and blood loss during OLT comparing ROTEM guided transfusion therapy versus conventional coagulation therapy were also analyzed. Due to the non-normality of the data, nonparametric Wilcoxon rank-sum tests were used to test for significant differences between the two groups in terms of the use of the 5 different blood products and blood loss. The sum of pRBCs, FFP, platelets, cryoprecipitate, and Cell Saver in units was used as an indicator of total blood product use. Results are expressed as medians and interquartile ranges. A two-tailed P value <0.05 was considered significant.

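### The SAP filed for this trial describes a different primary outcome, setting, product total, test and sample size from the protocol, and nothing reconciles them

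*SAP*

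**What the plan says.** The two documents share a title and an NCT number. The protocol is dated 01/09/2017 and the SAP 3/10/2020.

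**Protocol.** The population is hospitalised patients with cirrhosis and coagulopathy having endoscopic or neurosurgical procedures. The primary objective (III.C) reads: "To compare the total amount of pre-procedure blood products transfused between the ROTEM-guided transfusion protocol and conventional, laboratory-based transfusion protocol". On size, III.D says that "a total sample size of 202 patients (101 patients in both the non-ROTEM and ROTEM groups) is required to achieve 80% power". That calculation assumes a doubling in the geometric mean, compared by two-sample t-test at two-sided 0.05. Section III.F names a t-test and ANOVA for product use, bleeding events and hospital stay. The three secondary objectives are bleeding events, length of stay and hospitalisation costs.

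**SAP, Statistical Analysis.** On size: "Our sample size of thirty-four patients per group was based on a pilot project at OSUWMC that evaluated a total of sixteen patients". On the primary outcome: "We powered our study for the primary outcome of intra-operative blood loss based on the results of the pilot data". On setting: "Blood product usage and blood loss during OLT comparing ROTEM guided transfusion therapy versus conventional coagulation therapy were also analyzed". On the product total: "The sum of pRBCs, FFP, platelets, cryoprecipitate, and Cell Saver in units was used as an indicator of total blood product use". On stay: "Due to the non-normality of all laboratory values and ICU length of stay, nonparametric Wilcoxon rank-sum tests were used to test for significance". Wilcoxon rank-sum tests are also used for the individual products and for blood loss.

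**The concern.** A SAP should tell the reader how the protocol's primary hypothesis is tested. This one names another primary outcome in what appears to be another operation, and leaves the protocol's primary and secondary objectives without an analysis. Two readings are open, and both need correction.

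- **The SAP is this trial's.** Then the primary outcome, product total and test have changed and the sample size has fallen to a third, without explanation. The SAP is in the past tense and reports non-normality as an observed fact, so the choices appear to have been made after data were seen. A switch of outcome or test cannot be excluded.
- **The SAP belongs to another study.** Then the protocol's 101 per group stands, and this trial has no analysis plan beyond the brief III.F and the t-test named in III.D.

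**Working it through.** **1. The documents side by side**

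| Item | Protocol | SAP |
|---|---|---|
| Primary outcome | Total pre-procedure blood products (III.C) | Intra-operative blood loss |
| Setting | Endoscopy or neurosurgery | OLT, not defined; apparently liver transplantation |
| Product types | Pre-procedure codes: FFP, platelets, cryoprecipitate (Appendix 1) | Those three plus pRBCs and Cell Saver |
| Test for product use | t-test on geometric means (III.D); t-test and ANOVA (III.F) | Wilcoxon rank-sum |
| Stay | Hospital | ICU |
| Size | 101 per group, 202 in total | 34 per group, 68 in total |

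The documents agree on title, NCT number, a 16-patient pilot (8 + 8 in III.D), a two-sided 0.05 level, and the comparison of ROTEM with conventional management.

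**2. Can the SAP's variables be built from the protocol's data list?** No. In Appendix 1, peri-procedure blood loss is a yes/no item, which cannot give the medians and interquartile ranges that the SAP reports. Cell Saver and ICU stay are not listed. Red cells are listed only post-procedure.

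**3. Does the SAP cover the protocol's objectives?** No. It has no analysis of pre-procedure transfusion, bleeding events, hospital stay or costs. Outside its title it does not mention endoscopy or neurosurgery.

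**4. Sample sizes.** 68/202 = 0.34. Neither primary size can be reproduced. The SAP gives no effect, SD or power for 34 per group, and the protocol gives no SD for 101. The protocol's figure can only be inverted:

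- Effect on the natural-log scale: ln 2 = 0.693.
- Standardised difference giving 80% power with 101 per group (noncentral t, two-sided 0.05): d = 0.396.
- Implied log SD = 0.693/0.396 = 1.75.

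**5. Conditional illustration: 34 per group applied to the protocol's endpoint.** Neither document states this combination. It assumes equal log SDs in the two arms.

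- At log SD 1.75 the noncentrality is 0.396 × √(34/2) = 1.63. The normal approximation gives Φ(1.63 − 1.96) ≈ 37%, and the exact t-test 36%.
- With 34 per group, 80% power needs d = 0.690, so the detectable ratio is exp(0.690 × SD).

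| Log SD | t-test power at 34 per group | Ratio detectable at 80% power | Simulated Wilcoxon power |
|---|---|---|---|
| 1.0 | 80% | 2.0 | 78% |
| 1.5 | 47% | 2.8 | 44% |
| 1.75 (implied) | 36% | 3.3 | 33% |
| 2.0 | 29% | 4.0 | 28% |

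The Wilcoxon column comes from 10,000 simulated lognormal trials per SD, without ties or zeros. Repeat simulations gave up to 35% at log SD 1.75. A size of 34 per group suits a twofold ratio only if the log SD is near 1.0, which contradicts the protocol's own 101.

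**The case against.** The strongest reply is that the wrong file was uploaded. Section III.F mentions the team's own retrospective ROTEM study in liver transplantation, and III.D says the transfusion cutoffs were designed for transplantation. If so, this trial has had no outcome switch, no test conflict and no post hoc plan, and the power illustration falls away. This is plausible, but the documents do not settle it. The matching pilot size of 16 points the other way. Misfiling would also leave the trial without a SAP of its own.

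Three narrower points stand as qualifications:

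- **Red cells.** No protocol prose lists the products in the primary total. The absence of pRBCs rests on one coding row in Appendix 1, and the transfusion protocols in Appendices 2 and 3 are not readable in the supplied text. Cell Saver and the intra-operative window are firmer mismatches.
- **Power figures.** They combine the SAP's size with the protocol's endpoint and an SD that neither document gives. Products are recorded in whole units and given only if indicated, so ties and zeros are likely. With an assumed 30% zeros in each arm, simulated Wilcoxon power at log SD 1.75 falls to about 12%. The Wilcoxon column is therefore a rough guide.
- **The 80% statement.** It was a planning calculation for 202 patients, and smaller enrolment would not make it wrong as a record of that plan. It would stop describing the trial as run.

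**Conclusion.** The concern holds, and the mismatch must be fixed. The conflicts on primary outcome, setting, test and sample size are direct textual contradictions and need no calculation. The product-total conflict is clear for Cell Saver and the time window, and rests on the Appendix 1 codes for red cells. The documented size of the discrepancy is 68 patients against 202.

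The power figures (about 36%, range 29% to 80%) apply only if 34 per group is this trial's size and the protocol's endpoint is the one tested. They rest on a back-solved or assumed SD. Whether the SAP was misfiled or records a changed plan cannot be decided from the documents.

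**What to change.** 1. Establish whether text from another study was filed under this NCT number, and say so.
2. Replace or reconcile the SAP so that it analyses total pre-procedure blood products (III.C) and the three secondary objectives: bleeding events, hospital stay and costs.
3. State one primary outcome, one product-total definition (which products, which time window), one primary test and one sample size.
4. If the SAP is this trial's and Wilcoxon stays as the primary test, document when and why it replaced the protocol's t-test on geometric means, which came first.
5. If 34 per group is the actual size, withdraw the 80% power statement as a description of the trial, explain the change from 101, and give the assumed SD and effect. The planning calculation for 202 can stay as history.
6. Label any endpoint or test chosen after data were seen as post hoc. A rewrite now cannot restore pre-specification.

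The cost is document work, with no extra patients or procedures. The power statement may become less favourable, and some analyses may have to be reported as post hoc.

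### No planned summary shows how many units each strategy uses: add mean pre-procedure units per patient by arm, with a confidence interval, beside the planned test

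*SAP*

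**What the plan says.** Protocol III.C gives the primary objective as "To compare the total amount of pre-procedure blood products transfused" under the two strategies. The hypothesis in III.B is that ROTEM guidance "will significantly decrease blood product usage without any increase in procedural bleeding complications".

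Three passages bear on how usage will be compared:

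- **Protocol III.D** sizes the trial at 101 per arm, for 80% power with a two-sample t-test, to "detect a 100% increase in the geometric mean of the non-ROTEM group" over the ROTEM group. That is a log-scale comparison.
- **Protocol III.F** names a t-test and ANOVA for blood product usage. It does not say whether units are analysed raw or logged.
- **SAP, Statistical Analysis** sums five products in units per patient, compares arms by Wilcoxon rank-sum because the data are not normal, and states: "Results are expressed as medians and interquartile ranges".

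Neither document plans a mean per arm, a difference or ratio of means, or a confidence interval for the effect on usage. III.F also expects the FFP transfusion rate to halve, cryoprecipitate to rise, and overall product use to fall. III.E says products are given only where the transfusion protocol indicates them, so some patients may receive none.

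**The concern.** Total units used by an arm equal the arithmetic mean units per patient times the number of patients. A rank-sum test asks whether a patient in one arm tends to use less than a patient in the other. A median or geometric mean describes typical use. All three give limited weight to the few heavily transfused patients, who can account for a large share of the units.

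These measures agree with the mean when one arm is a constant multiple of the other. They can part when the arms differ in shape. That is possible here, because one product is expected to fall, another to rise, and some patients may receive nothing. A significant result could then be read as a saving in product when no units were saved. Even without such a reversal, the planned output would not give the mean number of units saved per patient, with its uncertainty.

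**Working it through.** **1. The plan's own figure.** Inputs from III.D: ratio of geometric means 2 (ln 2 = 0.693), two-sided 0.05, power 80%, 101 per arm. The log-scale SD is not stated, so it can only be back-solved.

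n per arm = 2 × (SD / ln 2)² × (1.960 + 0.842)²

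SD = 1.758 gives 2 × 6.433 × 7.849 = 101. The exact t-test solution is SD = 1.75. The SAP's 34 per group comes with no effect size, SD or power and cannot be reproduced.

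**2. When the measures agree.** For lognormal data, arithmetic mean = geometric mean × exp(SD²/2). With the same log SD in both arms the exponential term cancels, so a geometric-mean ratio of 2 is also an arithmetic-mean ratio of 2. There is no conflict in that case.

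**3. When they part: log scale.** Assume log SD 1.75 under conventional therapy, and geometric means of 2 (conventional) and 1 (ROTEM). Equal arithmetic means need a ROTEM log SD of √(1.75² + 2 ln 2) = 2.11, about 21% larger:

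- conventional: 2 × exp(1.75²/2) = 9.25
- ROTEM: 1 × exp(2.109²/2) = 9.25

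Share of 4,000 simulated trials declaring ROTEM significantly lower, although the true means are equal:

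| Test | 101 per arm | 34 per arm |
|---|---|---|
| Rank-sum | 70% | 29% |
| t-test on logs | 72% | 31% |
| Welch t-test on raw units | 6% | 4% |

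A hand example: every control patient uses 4 units; half the ROTEM patients use 1 and half use 7. Both means are 4. The geometric means are 4 and √(1 × 7) = 2.65, a ratio of 1.51 in ROTEM's favour. This example bears on geometric means only; the rank-sum test favours ROTEM in only about 8% of such trials at 101 per arm.

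**4. When they part: unit counts with zeros.** Assume control units are 1 + Poisson(1), with mean 2. In the ROTEM arm 70% receive none and the rest follow Poisson(8), so the mean is 0.30 × 8 = 2.4, which is 20% more. Results over 2,000 simulated trials with a two-sided rank-sum test at 0.05:

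| Patients per arm | Rank-sum significantly favours ROTEM | Same, and observed ROTEM total is at least the control total |
|---|---|---|
| 101 | 99.7% | 85% |
| 34 | about 82% | about 53% |

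With 40% of ROTEM patients at Poisson(5), the means are equal (0.40 × 5 = 2). The rank-sum test then favours ROTEM in about 91% of trials at 101 per arm and 54% at 34.

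**5. The price of testing means.** Assume a true mean ratio of 2 and equal coefficient of variation (CV) in both arms. Setting the control mean to 1 and the ROTEM mean to 0.5:

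n per arm = CV² × (1 + 0.25) × 7.849 / 0.25

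This gives 40 at CV 1, 157 at CV 2 and 354 at CV 3. The lognormal case with log SD 1.75 has CV = √(exp(1.75²) − 1) ≈ 4.5 and needs about 800. The documents give no raw-scale mean or SD to choose among these.

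**The case against.** **The total may be a per-patient quantity.** Appendix 1 records units per patient, and the SAP calls its five-product sum an indicator of total use. On that reading, ranks or logs do compare the stated variable. This is a fair reading of the variable. It still leaves a hypothesis about decreased usage without an estimate of how much less is used.

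**III.F's t-test may already compare means.** On raw units it would. A reader might therefore infer too much from a statement that the plan never targets means; the documents do not support that. Equally, they do not show that it does: the scale is unstated, III.D implies logs, and the later SAP uses ranks.

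**A reversal is not shown to be likely.** This stands. III.F expects overall use to fall, and does not say that the patients spared FFP differ from those given cryoprecipitate. The unit-count example is extreme: its control log SD is about 0.5, against the 1.75 implied by III.D. The planned IQRs would also reveal its tail (ROTEM median 0, IQR 0 to 5; control 2, IQR 1 to 3). The rank-sum test comes from the SAP, so the figures at 34 per group belong beside those at 101.

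**The SAP text may have to be replaced anyway.** It describes usage and blood loss during OLT, not pre-procedure units before endoscopy or neurosurgery. That is a separate problem. Resolving it would not by itself add a mean-based estimate.

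**Conclusion.** The gap is real and modest. No passage commits to estimating the mean units used per patient, or to giving a confidence interval for the effect on usage. A significant rank or log-scale result would therefore not by itself establish that fewer units were used.

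The figures (over 99% at 101 per arm and about 82% at 34, with ROTEM using 20% more) show that the disagreement can be large. They rest on assumed distributions and say nothing about how probable it is in this trial. Under a pure multiplicative shift there is no disagreement.

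Two stronger readings go too far. A reader might infer that the trial is likely to declare a false saving; the documents contain no usage data by arm that would show this. A reader might also infer that the mean must become the sole primary measure and the gate for any conclusion. The back-solved log SD suggests heavy skew, and under it a comparison of means could need about 800 per arm where 101 are planned. That is a trade-off, not an error in the planned test. The point is best classed as a cheap improvement.

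**What to change.** Keep the planned primary test, and state its scale. Beside it, add to the SAP:

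- mean pre-procedure units per randomised patient in each arm, counting patients who received none as zero;
- the difference in means, and the ratio, each with a 95% bootstrap or robust confidence interval;
- a sentence that any claim of decreased usage will be interpreted together with this estimate.

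The cost is a short SAP paragraph and a few lines of code. Appendix 1 already collects pre-procedure units, so no new data are needed. The drawback is that the interval may be wide if a few patients use many units, and the trial was not sized for it. The SAP should say so, so that an imprecise mean difference is not read as evidence of no effect.
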